### **Ethical Issues**

Ethical approval will be obtained from the BLINDED University Human Research Ethics Committee (HREC). Autonomy of participation or withdrawal, the anonymity of participants, and confidentiality of information collected for research reasons will be assured in the consent form and sustained all through study. The study is unlikely to involve any harm, risk or discomfort to participants. Patients' questions will be answered by the researcher honestly and as fully as possible. Completed questionnaires and signed consents of participants will be

securely stored during and after study completion in a locked cabinet on hospital premises for a period of 5 years after publication. The participants in the control group will receive a copy of the SADL-eM at the end of study with explanation from the researcher.

### **Protocol amendments**

The researchers will communicate important protocol modifications such as changes to eligibility criteria, outcomes, and analyses to HREC of BLINDED University under the regulations of the Helsinki Declaration.

### **Access to data**

Anonymized data will be available for peer review or quality appraisal. Any other data sharing will require the approval of the three researchers, as well as ethical approval from the requesting party.

### **Dissemination policy**

The study manuscript will be submitted for publication in a relevant peer-reviewed journal, and further dissemination through conference presentations. The SADL-eM will be made freely available on the XX University website in Arabic, with a summary in English.

### **COVID-19 precautions**

The treating occupational therapists and research assistant will follow the required COVID-19 precautions published by the WHO (DiSilvio, et al., 2020) and applied by each facility. This includes use of medical disposable gowns, disposable latex gloves, face shield, surgical mask, and hand hygiene using alcohol 70% or alcohol gel. These supplies will be provided by each facility as requirements of usual treatment.

### **Discussion**

Providing occupational therapy patient education that aim to improve the performance of patients with SCI in their ADL can optimize the outcomes of rehabilitation. The SADL-eM is an evidence-informed manual that supports a client-centred approach and aims to teach patient with SCI how to handle their ADL after injury and during inpatient rehabilitation phase. Quality and well-controlled clinical trials are essential to develop effective interventions for people with SCI. This randomized clinical trial aims to evaluate the impact of the SADL-eM intervention with SCI patients in inpatient rehabilitation setting in the Gaza strip, Palestine. If

the SADL-eM is demonstrated to be clinically effective, it will have significant implications for occupational therapy research and practice.

### **Trial status**

Recruitment is expected to start by March 2021 and is due to continue until the February 2022. The pilot study will start in January 2020.

### **Abbreviations**

ADL: Activities of Daily Living, SCI: Spinal Cord Injury, SCIM-III: Spinal Cord Independence Measure-III, SCIM-SR: Spinal Cord Independence Measure-Self-Reported, SADL-eM: SCI ADL Educational Manual

### **Competing interests**

The authors declare that they have no competing interests.

### **Funding**

This study protocol received no specific grant support from any funding agency in the public, commercial, or not-for-profit sectors.

### **Acknowledgements**

The researchers acknowledge all endeavors devoted to achieve this protocol.

**Figure 1. Study Flow Diagram (CONSORT Statement) **dummy****

## Random Number Table

[Random Number Generator](#) | [Frequently-Asked Questions](#) | [Sample Problems](#)

### 46 Random Numbers

43 13 12 81 57 53 75 09 68 07 74 35 14 90 31 25 66 56 59 80 86 20 58 60 77 03 85 45  
73 50 84 55 19 36 33 42 16 70 01 91 28 34 39 24 69 04

**Specs:** This table of 46 random numbers was produced according to the following specifications: Numbers were randomly selected from within the range of 1 to 92. Duplicate numbers were not allowed. This table was generated on 8/19/2020.

**Figure 1: Random generated numbers of intervention group**

## **Box 1: inclusion and exclusion criteria**

Inclusion criteria
▪ Confirmed SCI diagnosis by computed tomography or magnetic resonance report.
▪ ASIA: A, B, and C
▪ Age between 18 and 65 years old.
▪ Stable medical condition.
▪ Time elapsed after SCI is not more than 6 months.
▪ Minimum time of stay in inpatient rehabilitation unit is six weeks.
▪ Active involvement in rehabilitation program.
▪ Sufficient comprehension (read/write) of the Arabic language.
Exclusion criteria
▪ Unconfirmed diagnosis.
▪ Patients who have communication and/or cognitive disorders such as global aphasia and memory deficit.
▪ Patients with disturbed level of awareness such as coma or lethargy.
▪ Time elapsed since SCI is more than 6 months.
▪ ASIA: D and E
▪ Unstable medical condition.
▪ Patients who have other cause(s) of disability in addition to SCI such as stroke or amputation.
▪ Age less than 18 or more than 65 years old.
▪ Time of stay in inpatient rehabilitation unit is less than six weeks.
▪ Inactive involvement in rehabilitation program.
▪ Patients with a progressive disease or a psychiatric condition that would interfere with active participation in rehabilitation program.
▪ Patients with cardiovascular contraindications.
▪ Persons who become walking ambulatory during the inpatient period.
▪ Persons with complete tetraplegia C4 or above.
▪ Persons on mechanical ventilator.

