for patient education) and patient readiness (motivation and interest) are two important concerns for effective patient education. Time allocated for patient education can be limited and inadequate due to patient treatment workload and staffing shortages. Decreased motivation and interest of the patient during rehabilitation adds another barrier to patient education (Shepherd, et al., 2012).

This study plans to evaluate the impact of providing an evidence-informed SCI ADL educational manual (SADL-eM) on activities of daily living among people undergoing rehabilitation for a spinal cord injury in the Gaza Strip, Palestine. This study may counter the effect of decreased LOS in rehabilitation in this LMIC context. By improving patient education, the authors intend to improve patients' involvement in their treatment during their stay in the three inpatient rehabilitation settings available in the Gaza Strip. An effective educational intervention will enhance the quality of care and reduce the cost of healthcare services in the long term.

This aim of the proposed study is to evaluate the impact of a SADL-eM on activities of daily living. This educational intervention is delivered to inpatients with SCI in a rehabilitation setting.

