The purpose of the SADL-eM is to serve as a treatment tool during inpatient rehabilitation. Over the first week of admission of each person with SCI in each facility, a research clinical supervisor will recruit study participants based on the study eligibility criteria, obtain consent, and assign each consenting patient to one of the two study groups. They will then provide each participant in the intervention group with a SADL-eM hard copy, and explain the purpose of the manual and how to use it. The manual will be reviewed by the treating occupational therapist and the person with SCI during their treatment sessions. During occupational therapy sessions, the therapist will refer to the relevant chapter of the manual. The therapist will also indicate to the participants which parts of the manual are not relevant to them (based on their gender, driving status, or level of SCI). Participants' queries on the content of the manual will be answered by the treating occupational therapist. The therapist will include the manual in as many SADL-eM educational sessions as required, but not less than three sessions per week with 15 minutes per session. The minimum level of clinical experience of each treating occupational therapist will be two years. Good Arabic language comprehension, and the ability to read and write is mandatory for both therapists and patients. No other special skills or experience are required.

The participants will keep the manual to review after sessions and after discharge from the inpatient rehabilitation setting. For the purposes of the study, blinding and bias reduction, the therapists and the participants in the intervention group must not share any part of the manual or information included with other patients or staff. The research assistant who performs data collection, the clinical supervisor, and occupational therapy team will be invited for informational session prior to data collection in each of the participating settings. The informational session will focus on the study purpose, recruitment, eligibility criteria, use of

the SADL-eM, roles, bias reduction, and blinding. Use of data collection tools will take place in a separate session with the research assistant. The principal researcher will answer all questions of the research team during informational sessions and during the research.

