For the purposes of the current study, the SADL-eM will be provided during face-to-face individual occupational therapy sessions without any constraints regarding treatment area. It could be occupational therapy department, patient ward, and educational activities room. The face-to-face manual delivery does not require any infrastructure or special equipment.

The number of sessions, time allocated, and frequency are determined by each therapist and participant. Determinants may include participant's capabilities, potentials, and progress during treatment; and the scope of the service such as time allocated for each patient, therapist-patient ratio, and frequency of inpatient sessions. The therapist and the participant will continue to use the manual during treatment sessions until they decide there is no need for further use of the manual or the participant is discharged. Treating occupational therapists will retain records of any change or modification of the SADL-eM administration. The researchers will conduct a pilot study in a similar sample of 15 S people with SaCIs to improve the use of intervention and data collection tools.

Nonadherence to medical treatment in clinical trials of medical efficacy has serious consequences on the quality of research. It may obscure data collected and disrupt findings obtained (Quittner, et al., 2000). The steps to ensure adherence to the intervention during study include clearly defining the intervention, measuring, and then comprehensively reporting adherence to the intervention. Attendance records collected by the therapist (times, duration, and intensity of treatment; manual elements covered) and SADL-eM adherence therapist-report questionnaire will be used to measure and report adherence to the SADL-eM intervention. The manual will be made freely available on the Stellenbosch University website when the research is complete.

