## **Data Collection**

All admitted SCI patients will be evaluated by the research supervisor in the setting for eligibility within three days of admission to the inpatient rehabilitation setting, until the desired sample size is reached. Eligible individuals will sign a consent form and then be assigned randomly to one arm of the study by the research supervisor. The allocation sequence will be concealed from patients, therapist and, assessor. The data about exposure to the educational intervention will be collected by a separate research assistant by phone and will be concealed

from the assessor. Each occupational therapy department will assign four therapists to follow up the trial cases – two for the intervention and two for control group. All the staff in the occupational therapy department, participants, and assessors will be requested not to discuss the trial and intervention material between them. The importance of concealing any information until the end of the study will be explained. Study participants are not allowed to switch between occupational therapists or study arms. They will be asked not to participate in other educational interventions (peer or external) related to their rehabilitation or seek treatment outside their trial. The head of occupational therapy department within each rehabilitation setting will supervise participants and assigned occupational therapists in both study arms to reduce contamination bias such as sharing intervention content with the control group, sharing similar time and space of occupational therapy sessions, and exchange of therapists.

Contamination bias due to already existing background and/or receipt of additional educational interventions will be measured within each arm of the study (Chi-Square test to compare the progress means). However, no case will be eliminated from statistical analysis due to contamination bias.

The study will adopt approaches to prevent loss of participants to follow-up by making questionnaires as easy to complete as possible, providing incentives in the form of a free copy of the educational manual for the control group, and explaining the importance of the study (Magill, et al., 2019).

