## **Data Analysis**

Captured data will be coded and reviewed by the researchers for clarity and completion. A spread sheet will be prepared by the three researchers and then loaded to IBMSPSS 21 for analysis. The first author will perform data entry. The research assistant will check the data entry using the original forms, and the research supervisor will check the data for missing data and entry errors.

The following statistical methods will be used to test the research hypothesis:

- a. To describe participants' characteristics: descriptive statistics such as frequency, percentage, mean with standard deviation for Normally distributed data and median and Inter Quartile range will be used for continuous variables that are not Normally distributed will be used.
- b. Missing values will not be substituted. Intention-to treat analysis method will be used for analysis.
- c. To determine the significance of biographical variables at baseline: McNemar and Chi Square with Nominal variables, T-test and Mann-Whitney for interval variables will be used.
- d. To compare the efficacy of the educational manual: Repeated Measures ANOVA/ Linear Mixed Models will be used will be used to assess differences between intervention and control group using the ADL data. The Repeated Measures ANOVA and Linear Mixed Models will be used to analyze the data. Linear Mixed Models has advantage in dealing with missing values and provides fixed and random effect (Krueger and Tian, 2004).
- e. Adherence to the intervention will be summarized using frequency and percentage.

All the data collected and entered (hardcopy and soft copy) will be securely stored by the first researcher in a locked cabinet on hospital premises (hardcopy) and in a password-protected file online.

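### Box 1 makes an actual stay of six weeks a condition of entry, which cannot be known at randomisation, and the plan does not say how randomised patients who leave earlier are assessed or analysed

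*Combined protocol and SAP*

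**What the plan says.** Box 1 states the length-of-stay rule twice. The inclusion line reads "Minimum time of stay in inpatient rehabilitation unit is six weeks" and the exclusion line reads "Time of stay in inpatient rehabilitation unit is less than six weeks". Neither refers to a planned or expected stay.

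Under Data Collection, the research supervisor evaluates each admitted patient "for eligibility within three days of admission to the inpatient rehabilitation setting". The order of events follows: "Eligible individuals will sign a consent form and then be assigned randomly to one arm of the study". The section on the manual puts recruitment, consent and assignment in the same period: "Over the first week of admission of each person with SCI in each facility".

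The outcome assessment is a face-to-face interview six weeks after the admission assessment (Data Collection). Data Analysis item b says that missing values are not replaced and that "Intention-to treat analysis method will be used for analysis". Item d names repeated-measures ANOVA and linear mixed models without choosing between them; the Abstract names only repeated-measures ANOVA.

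The manual is to be used in sessions "until they decide there is no need for further use of the manual or the participant is discharged", so discharge is foreseen, but no rule covers discharge before week 6. The Introduction gives shortened stays as part of the reason for the trial: "This study may counter the effect of decreased LOS in rehabilitation in this LMIC context".

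**The concern.** A stay of six weeks is a fact that exists only on day 42. It is used as a criterion on day 3, with assignment by about day 7. A site that follows Box 1 to the letter would have to reclassify a randomised patient as ineligible on the day he or she goes home in week 4 or 5. That is an exclusion after randomisation, and it contradicts intention to treat.

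Even if no site does this, the patient can be lost in practice. The week-6 interview is face to face, no provision is made for doing it after discharge, nothing is imputed, and repeated-measures ANOVA drops anyone without a week-6 value.

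At stake is the SCIM-SR comparison. If the time of discharge is related to ADL recovery, which is the outcome, or differs by arm, the patients left in the two arms are no longer comparable. There is also a question of scope: a trial motivated partly by short stays would describe only patients with longer ones.

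**Working it through.** **1. Timing.** Six weeks is 42 days. At the day-3 eligibility check the stay criterion lies 42 − 3 = 39 days ahead; at the end of the first week, 42 − 7 = 35 days ahead. No reading of the word actual allows the rule to be applied at either point. Box 1 also contains a line excluding persons who become walking ambulatory during the stay, which can only be met after entry. So the box is not purely a screening list, and a literal reading of the stay lines is not far-fetched.

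**2. The plan's own sample size.** The section on participants and sample size gives 90 patients, 45 per arm, for an effect size of 15%, 80% power and a 5% error level. Three things are not stated and are assumed here: 15% means Cohen's f = 0.15, the correlation between the two time points is ρ = 0.5, and the test is two-sided. For the group-by-time interaction with m = 2 time points:

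λ = f² × N × m / (1 − ρ) = 0.0225 × 90 × 2 / 0.5 = 8.1, on 1 and 88 degrees of freedom, which gives power 0.804.

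The figure of 90 reproduces, with no room for loss: 88 evaluable patients already give 0.795. The documents give no rate of early discharge, so a range is assumed:

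| Lost | Evaluable | λ | Power |
|---|---|---|---|
| 10% | 81 | 7.29 | 0.760 |
| 20% | 72 | 6.48 | 0.709 |
| 30% | 63 | 5.67 | 0.649 |

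**3. Bias if early discharge is related to recovery.** All inputs are assumptions. The outcome is N(0, 1) in control and N(0.5, 1) in intervention. A latent early-discharge score has correlation r with the outcome. A patient leaves early if the score exceeds t, with t set so that a share p of controls leave. Write h(x) = φ(x)/Φ(x). Among retained patients:

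- control mean = −r h(t)
- intervention mean = 0.5 − r h(s), with s = t − 0.5r
- difference = 0.5 − r [h(s) − h(t)]
- share lost in the intervention arm = 1 − Φ(s)

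Example with r = 0.7 and p = 30%: t = 0.5244, s = 0.5244 − 0.35 = 0.1744, h(t) = 0.4967, h(s) = 0.6903. The difference is 0.5 − 0.7 × 0.1936 = 0.3645, and 43% of the intervention arm is lost.

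Estimated effect in SD, with the share of the intervention arm lost in brackets:

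| r | p = 10% | p = 20% | p = 30% |
|---|---|---|---|
| 0.7 | 0.417 (18%) | 0.385 (31%) | 0.365 (43%) |
| 0.5 | 0.460 (15%) | 0.443 (28%) | 0.433 (39%) |
| 0.3 | 0.486 (13%) | 0.480 (24%) | 0.476 (35%) |
| 0 | 0.500 (10%) | 0.500 (20%) | 0.500 (30%) |
| −0.3 | 0.488 (8%) | 0.482 (16%) | 0.478 (25%) |
| −0.5 | 0.468 (6%) | 0.452 (14%) | 0.441 (22%) |
| −0.7 | 0.441 (5%) | 0.410 (12%) | 0.388 (19%) |

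For non-zero r the estimate lies between 0.365 and 0.488 SD, an attenuation of about 2% to 27%. At r = 0 there is none. The sign of r decides which arm loses more patients.

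**4. Bias if early discharge differs by arm for other reasons.** Suppose removed patients score D above those kept, and shares pT and pC are removed from intervention and control. The kept mean in an arm falls by p × D, so the intervention-minus-control difference shifts by D × (pC − pT). With D = 0.5, pC = 20% and pT = 10% the shift is 0.05 SD; with D = 1.0, pC = 30% and pT = 10% it is 0.20 SD, with no true effect. Swapping the shares reverses the sign. The attenuation in step 3 is therefore a feature of that model and not a general result.

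**The case against.** The ordinary reading of a stay criterion checked at day 3 is the expected stay. The plan runs in the order eligibility, consent, assignment; it states intention to treat; and no section tells a site to re-apply Box 1 later. This stands in part. A reader might infer that the plan will remove early leavers, but it does not say so. What it contains is a literal rule that conflicts with the analysis statement, and no sentence that settles the matter.

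A reader might also infer that the best responders are removed and that the bias runs toward no effect. The documents do not support that. The Introduction describes limited resources, waiting lists and some patients going home with fewer ADL skills, which fits resource-driven discharge (r near 0) or even a negative r at least as well. Nor is there a source for saying that discharge is decided by staff who know the arm: treating therapists know it, but nobody is named as deciding discharge.

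On the rationale, the Introduction gives no number for a shortened stay, and six weeks could itself be one. The Discussion makes no claim about short-stay settings. Use of the manual until or after discharge is compatible with a six-week stay. What remains is narrower: patients with stays under six weeks are outside the trial on either reading of Box 1, and the plan does not explain how that fits its stated motive.

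Finally, the linear mixed model keeps a patient's baseline record. That helps, but the plan leaves the choice of model open, and a baseline record alone says nothing direct about the patient's week-6 status.

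**Conclusion.** The point holds as a faulty stated rule together with a missing follow-up rule. Box 1 cannot be applied when it is needed; taken literally it conflicts with intention to treat; and early leavers could drop out in effect even if nobody declares them ineligible. Whether this biases the comparison depends on how discharge relates to recovery and to arm, and the documents do not establish the direction.

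On the stated assumptions the size runs from no bias at zero correlation to an estimate of about 0.37 SD in place of 0.5 SD at the far end of the range. Loss of 10% to 30% would lower power from 0.80 to between 0.76 and 0.65, given f = 0.15 and ρ = 0.5. The early-discharge rates, the correlation, the 0.5 SD effect, f and ρ are assumptions. The timing conflict needs none of them. Deleting the walking-ambulatory line would not remove it.

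**What to change.** - In Box 1, replace the two stay lines with one criterion that can be judged before randomisation: an expected inpatient stay of at least six weeks, recorded before the arm is assigned.
- In Data Collection, state that every randomised patient stays in the trial whatever the date of discharge, and has the week-6 SCIM-SR and SCIM-III wherever he or she is. The blinded assessor should collect both. The assistant who telephones about exposure to the intervention should not, because that information is meant to be kept from the assessor.
- In Data Analysis, state that all randomised patients are analysed in the arm assigned, using the linear mixed model already named in item d.
- Limit the conclusion to patients expected to stay six weeks or more, or justify the criterion against the shortened-stay rationale in the Introduction. An expected-stay criterion still screens out short-stay patients, so the rewording alone does not answer this.

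The cost is a few lines of text and some assessments off the ward or by interview. SCIM-SR is self-reported, and the plan describes an interview form of SCIM-III taking about 20 minutes, so this is feasible. The mode of collection should be recorded, since it may differ between patients and between arms. The change has to be made prospectively, because a week-6 assessment that was not done cannot be recovered.

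### Box 1 excludes patients who start to walk during the inpatient stay; applied after randomisation, this contradicts the intention-to-treat statement, and no section settles which rule governs

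*Combined protocol and SAP*

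**What the plan says.** The exclusion list in Box 1 contains the line "Persons who become walking ambulatory during the inpatient period". The same box requires a stay of at least six weeks in the rehabilitation unit.

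On timing, the section on the SADL-eM manual says: "Over the first week of admission of each person with SCI in each facility, a research clinical supervisor will recruit study participants". In that same window the supervisor is to obtain consent and "assign each consenting patient to one of the two study groups". Data Collection says that admitted patients will be "evaluated by the research supervisor in the setting for eligibility within three days of admission to the inpatient rehabilitation setting", and that those eligible then consent and will "be assigned randomly to one arm of the study by the research supervisor". The outcome measures are taken on admission and six weeks later.

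On who is analysed, Data Analysis item b states an intention-to-treat analysis without substitution of missing values. The only explicit rule on keeping cases is in Data Collection: "no case will be eliminated from statistical analysis due to contamination bias". It covers contamination and nothing else.

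**The concern.** The walking line describes something that happens over the course of the stay, yet it sits in a list that is otherwise used to decide who enters the trial. Most of the stay lies after assignment. Staff who follow Box 1 literally would take out a patient who has already been randomised; an analyst who follows item b would keep that patient. Both instructions cannot be carried out, and the three hospitals could resolve the conflict differently.

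The event is not neutral. Starting to walk is a sign of recovery, and the primary outcome is self-reported independence in daily activities at six weeks. Box 1 admits ASIA C patients and injuries up to six months old, so later walking cannot be ruled out. Removing patients on a post-randomisation event linked to the outcome gives up the comparability that randomisation provides.

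The line could also be applied by someone who knows the arm. The research supervisor both judges eligibility and assigns patients, and the therapists are split, "two for the intervention and two for control group".

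**Working it through.** **1. How much of the period lies after assignment.** The minimum stay is six weeks = 42 days (Box 1). Assignment by the end of the first week leaves 42 − 7 = 35 days, or 35/42 = 83%. Assignment by day 3, the limit for the eligibility check, leaves 42 − 3 = 39 days, or 39/42 = 93%. A longer stay raises both shares. The line therefore acts mainly on patients already randomised.

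**2. The rules side by side.** Take a patient assigned on day 5 who starts to walk on day 25.
- Box 1, as written: excluded.
- Data Analysis item b: analysed in the assigned arm.
- Data Collection, rule on keeping cases: silent, because the reason is not contamination.
- Any section on follow-up of such a patient, or on taking the 6-week SCIM-SR: none.

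**3. The scale for an illustration.** The plan gives 90 patients, 45 per arm, an effect size of 15% and 80% power. Assumptions: 15% means f = 0.15 in the group-by-time test of a repeated-measures ANOVA with two time points, the pre/post correlation is 0.5, and the test is two-sided at 5%. The noncentrality is f² × N × 2/(1 − 0.5) = 0.0225 × 90 × 4 = 8.1, which gives 80.4% power at N = 90. On the change score, (45/2) × d² = 8.1 gives d = 0.6. With correlation 0.5 the SD of change is √(2 − 2 × 0.5) = 1 in units of the score SD. So 0.6 SD serves as the true effect. The plan states neither the reading of 15% nor the correlation.

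**4. Effect of removing walkers.** Further assumptions: normal scores; a latent walking tendency correlated r = 0.5 to 0.9 with the 6-week score; a cut-off c = 1.2816 that removes 10% of controls; the same treatment effect in walkers and non-walkers. The covariance of walking tendency with change is r − 0.5r = 0.5r. Write λ(x) = φ(x)/Φ(x), and let s be the share of the treatment effect that carries over to walking (1 = full, 0.5 = half, 0 = none). Then

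estimate = 0.6 − 0.5r × [λ(c − 0.6rs) − λ(c)], with λ(1.2816) = 0.195.

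| Scenario | r = 0.5 | r = 0.9 |
|---|---|---|
| Full shift | 0.6 − 0.25 × (0.2945 − 0.195) = 0.575 | 0.6 − 0.45 × (0.3931 − 0.195) = 0.511 |
| Half shift | 0.6 − 0.25 × (0.2414 − 0.195) = 0.588 | 0.6 − 0.45 × (0.2833 − 0.195) = 0.560 |
| No shift, applied alike | 0.600 | 0.600 |
| No shift, intervention arm only | 0.6 − 0.25 × 0.195 = 0.551 | 0.6 − 0.45 × 0.195 = 0.512 |
| No shift, control arm only | 0.6 + 0.25 × 0.195 = 0.649 | 0.6 + 0.45 × 0.195 = 0.688 |

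At full shift the intervention arm loses 16% (r = 0.5) to 23% (r = 0.9) of its patients.

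**5. What the no-shift row depends on.** The 0.60 holds only because the effect is assumed equal in walkers and non-walkers. Keep the overall effect at 0.6 with 10% walkers in each arm. If walkers gain 0, those who remain show 0.6/0.9 = 0.67. If walkers gain 1.2, they show (0.6 − 0.1 × 1.2)/0.9 = 0.53. Removal then changes the estimate even when the manual has no effect on walking.

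**The case against.** The strongest reply is that Box 1 is a screening list. Data Collection puts the eligibility check within three days of admission, then consent, then assignment, and item b promises intention-to-treat. If every line of Box 1 is applied at that check and never again, nothing conflicts. The stay and involvement lines are most naturally read that way. One could also take the inpatient period to mean an earlier hospital stay, since patients come from secondary care and readmissions are eligible.

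Part of this stands. A reader might infer that the plan drops walkers from the analysis. It does not say so, and the contradiction arises only if the line is applied after assignment. But a verb about becoming ambulatory during the inpatient period is hard to read as status at screening, and the earlier-stay meaning is no more natural. No other section limits the line to the time before assignment. If that is the intent, one clause would say it.

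A second reply is that an ADL manual is unlikely to change walking much: its chapters cover the team, daily activities, devices, home adaptation and knowledge, not gait. That is a fair reason to regard the full shift as an extreme case. At half the shift the loss is small. It does not answer uneven application or an effect that differs between walkers and non-walkers.

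**Conclusion.** The point holds in conditional form. Applied as written after assignment, the Box 1 line removes randomised patients on a recovery-related event and contradicts the intention-to-treat statement. The documents leave open which rule governs. This should be fixed before recruitment.

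A reader might go further and conclude that the trial will understate the manual's benefit. The documents do not support that: they give no walking rate and no effect of the manual on walking, so neither size nor direction is known. The illustration shows only what could happen with a true effect of 0.6 SD, a pre/post correlation of 0.5, 10% of controls removed and one common effect. The estimate is about 0.60 SD if walking is unaffected and the line is applied alike, 0.59–0.56 at a half shift, 0.58–0.51 at a full shift, and anywhere from 0.51 to 0.69 if only one arm loses its walkers. Other inputs would give other figures.

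**What to change.** Reconcile Box 1 with the manual section, Data Collection and Data Analysis item b.

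1. State in Box 1 that all criteria are applied once, before randomisation. The authors should word the walking line to match, and the stay line as expected stay.
2. Add to Data Analysis item b: *All randomised patients are followed and analysed in their assigned arm; none is removed because of later walking, discharge or involvement, and these events are reported by arm.*
3. If a result without walkers is of interest, show it as a labelled supplementary analysis.

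The cost is a clause in Box 1 and a sentence in Data Analysis, with no extra patients or visits. The downside is that the main result covers a somewhat broader group than Box 1 now describes; the supplementary analysis shows the narrower one.
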